4.2 Study Tasks

Stage One Tasks

- Iterative usability testing of the ATFS for supporting socket design, informing its further development.
- Iterative development of ATFS training materials.
- Design sockets for patients from NHS clinics, provided by Opcare, with the aid of the ATFS.
- Capture outcome measures (e.g., socket comfort scores).
- Explore prosthetists' views and experiences of using the ATFS in their current practice and pathways.
- Evaluate the strengths and weaknesses of the ATFS.
- Integrate findings from qualitative research to further understand experiences from the clinician's perspective to support the development of the ATFS.

North Bristol NHS Trust

Stage Two Tasks

- Usability testing of the final developed ATFS.
- Design sockets for patients from NHS clinics, provided by Opcare, with the aid of the ATFS.
- Capture outcome measures (e.g., socket comfort scores, time taken for initial rectification and socket design using the ATFS for comparison with the standard CAD/CAM socket design process).
- Explore prosthetists' views and experiences of independently using the ATFS in their current practice and pathways.
- Integrate findings from qualitative research to demonstrate safe and efficient clinical usability of the ATFS.

6. Methods and design

6.1 Population

This study will recruit two groups of participants in order to fulfil the research objectives.

The first group will be prosthetists at the three participating centres. This study will explore the experiences of the prosthetists designing sockets with the aid of the ATFS in-clinic, comparing to the standard design workflow used in their prosthetics centres, plus their views on any barriers or facilitators to using the ATFS. These perspectives are vital to ensure that the ATFS is clinically translatable and as useful as possible in supporting the prosthetists' expert socket design process.

The second group will be adults who have undergone a transtibial (i.e. below knee) amputation and are attending the Bristol, Cambridge or Norwich NHS Opcare prosthetic services centres. The study focus will be the design of sockets for below knee amputation, as this has the highest prevalence⁷ and as such has been the focus of researchers for CAD/CAM software development^{8, 9}. Also, transtibial socket designs are most suited to the ATFS method as they include the most inhomogeneous design features. It is also desirable to work with this patient group first for safety reasons, since individuals with transtibial amputation are less likely to have comorbidities compared to those using transfemoral sockets.

6.1.1 Inclusion and exclusion criteria

Group A – Prosthetists

Inclusion criteria

- Prosthetists working with patients recruited as participants in the study
- Are willing to design a socket using the ATFS

Exclusion criteria

- Not familiar with using CAD software technologies for socket design
- Unwilling to design a socket using the ATFS

283-04A-04_(XF)_Study Protocol IRAS ID: 317901 ERGO NO: 81419 HRA REC REF: 24/LO/0126 9

CONFIDENTIAL THIS DOCUMENT IS PROPRIETARY INFORMATION AND IS NOT TO BE REPRODUCED OR DISCLOSED WITHOUT PRIOR WRITTEN APPROVAL.

Group B – Adults with limb loss

Inclusion criteria

- Over the age of 18
- Have had a transtibial amputation
- Deemed ready to cast for a new prosthesis by the clinical team as per usual care at the prosthetic centre
- Able to understand verbal and written English and give informed consent

Exclusion criteria

- Contraindication to be fitted for a prosthetic socket
- Unwilling for their prosthetist to design their socket using the ATFS
- Unable to answer verbal questions (as per normal fitting appointment) on their socket fitting and comfort

6.2 Population size

Group A – Prosthetists

Prosthetists across the three NHS sites (up to 17 in total) will be recruited in the participating prosthetics centres, allowing several prosthetists' usability experiences to be captured. For Stage One (the iterative usability testing) BS-EN 62366 suggests that a sample size of 5-8 participants is sufficient. BS EN 62366 illustrates in Annex K that using small sample sizes identifies usability defects and reduces the required clinical resource.

A sample size of 15 participants is suggested according to BS-EN 62366 for the summative usability testing (Stage Two). This sample size gives a probability of capturing at least one occurrence of a usability defect of 91% (IEC/TR 62366-2:2016). A power analysis to determine sample size has not been carried out as BS EN 62366 discourages use of power analysis to determine sample size for usability studies.

A sample size of 17 was determined taking into account BS-EN 62366, the number of prosthetists at each of the NHS sites, allowing for 10% withdrawals, and matching similar published studies exploring clinician perspectives of socket fit¹⁰.

Group B – Adults with limb loss

A sample of convenience of up to 46 adults with transtibial limb loss will be recruited across the three participating prosthetics centres for this study. This sample size was determined by considering the number of usability study iterations that may take place, both patient and prosthetist withdrawals, and demonstration of the clinical usability within Stage Two.

Sample size was determined for the two stages as follows:

Stage One:

For each participating prosthetist in Stage One, one patient participant will be recruited per usability iteration. 5-8 prosthetists will participate in each usability testing iteration. Allowing for withdrawal

283-04A-04_(XF)_Study Protocol IRAS ID: 317901 ERGO NO: 81419 HRA REC REF: 24/LO/0126 10

CONFIDENTIAL THIS DOCUMENT IS PROPRIETARY INFORMATION AND IS NOT TO BE REPRODUCED OR DISCLOSED WITHOUT PRIOR WRITTEN APPROVAL.

North Bristol NHS Trust

and for three iterations, a maximum of 27 patient participants would need to be recruited. Less participants may be recruited if fewer usability iterations are required in Stage One as determined by the technology development process (e.g., feature freeze), and the participating clinicians being comfortable to use the ATFS throughout the full socket design process independently without resorting to their current socket design process (i.e. no further observation or detection of a usability problem).

Stage Two:

A sample size of 19 will be recruited for Stage Two. This sample size was determined using a noninferiority result for a crossover group trial with normal socket comfort score data. We determined an appropriate sample size of 19 for this group (power: 0.9, significance level: 0.025, Mean Difference: 0, non-inferiority limit: 1.21, population Socket Comfort Score standard deviation: 0.998). This was using the NIHR SampSize web tool with the non-inferiority limit obtained from Hafner et al¹¹ and population standard deviation obtained from the ATFS training dataset¹² which is an extension to the population presented in Dickinson et al⁶. An addition of 10% was added accepting the uncertainty around the employed data.

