4.1 Research Objective

Following the preceding study (IRAS ID: 313408, EGRO NO: 76033, REC REF: 22/YH/0215, 01/02/23 – 30/11/23), the objective of this study is to evaluate the clinical usability, in terms of safety and performance, of the Adaptive Templates Fitting System that combines Adaptive Templates technology with the experience and expertise of the clinician to provide optimal socket design support. It is important for this clinical investigation to verify the clinical safety and performance of the ATFS to comply with Section 1 of Annex I of the Medical Devices Directive; demonstrating when used for its intended purpose (support of socket design by prosthetists) the safety of patients (those receiving the designed sockets) will not be compromised.

The study will be carried out in two stages contextualised with longitudinal qualitative research, according to study design definitions from BS-EN 62366:

Stage One will explore the strengths and limitations of the in-clinic usability of the ATFS to inform its further development, reducing as far as possible the risk of use error due to user interface, and;

Stage Two will assess the in-clinic usability of the updated ATFS. This clinical investigation will verify the safety and efficiency of its in-clinic use by capturing:

- socket comfort scores of sockets designed using the ATFS to demonstrate non-inferiority compared to the current process (without the support of the ATFS) and socket comfort scores > 7, the NHS key performance indicator; and
- time taken for initial rectification and socket design using the ATFS compared to with the current process.

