This procedure matches normal care except that the socket will have been designed with the aid of the ATFS rather than the standard CAD/CAM socket design process for the clinic.

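### Stage Two is sized as a crossover non-inferiority trial but described as a single arm, so the stated power of 0.9 does not apply and the non-inferiority objective has no described comparator

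*Protocol*

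**What the plan says.** **Objective.** Section 4.1 lists, for Stage Two, "socket comfort scores of sockets designed using the ATFS to demonstrate non-inferiority compared to the current process (without the support of the ATFS"). Beside it stand comfort scores above 7 (the NHS key performance indicator) and design time compared with the current process. None of the three is ranked above the others.

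**Sizing.** Section 6.2 (Group B, Stage Two) states: "A sample size of 19 will be recruited for Stage Two". On the method it says: "This sample size was determined using a noninferiority result for a crossover group trial with normal socket comfort score data". The inputs are "power: 0.9, significance level: 0.025, Mean Difference: 0", a non-inferiority limit of 1.21 points, and "population Socket Comfort Score standard deviation: 0.998", taken from the ATFS training dataset. A further 10% is then added.

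**Conduct.** Section 6.6 says of the patient pathway: "This procedure matches normal care except that the socket will have been designed with the aid of the ATFS rather than the standard CAD/CAM" route used in the clinic. The patient tries one new socket, has it adjusted and takes it home. Section 6.5 makes Stage Two the same as Stage One apart from three changes: no thinking aloud, no software changes, and a different interview emphasis. Section 6.8 ends Stage Two when the ATFS has supported socket design for 19 patients. The E-CRF (Section 16.2) has one comfort-score item, plural and dated, and a time item for ATFS use.

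**The concern.** In a crossover, each patient contributes a difference between two conditions, and the formula's power is the power to bound the mean of those differences. The described procedures have no second socket, no second period and no order of allocation, so they yield no such differences. The sizing and the conduct therefore describe two different trials within one document.

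If this stands, the non-inferiority comparison has an ATFS mean but no stated current-process mean to set against it. The reference would have to be chosen later, possibly after the ATFS scores are known, and the power of 0.9 would be quoted for a comparison that was never set up.

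**Working it through.** **1. Inputs (Section 6.2).** Margin 1.21; SD 0.998; true difference 0; alpha 0.025 (sidedness is not stated; one-sided reproduces the figure); power 0.9; addition 10%.

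**2. Reproducing 19.** Take 0.998 as the within-patient SD.
- Normal approximation: n = 2 × 0.998² × (1.960 + 1.282)² / 1.21² = 14.3, so 15, or 17 after 10%. This is close but not a match.
- Noncentral t with n − 2 degrees of freedom and SE = 0.998 × √(2/n):
  - n = 16: SE 0.353, noncentrality 1.21/0.353 = 3.43, power 0.890
  - n = 17: SE 0.342, noncentrality 3.53, power 0.910
- 17 × 1.1 = 18.7, rounded up to **19**, an exact match. Power at 19 is 0.940.
- Reading 0.998 as the SD of the paired difference gives n = 10, or 11 after 10%, which does not match.

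So a crossover formula really was used, and it was computed correctly.

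**3. Data needed against data described.**

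| | Crossover as sized | Conduct as described |
|---|---|---|
| Sockets per patient | 2 | 1 (ATFS) |
| Condition scores | 17 × 2 = 34 evaluable; 19 × 2 = 38 recruited | ATFS socket only, 19 patients |
| Within-patient differences | at least 17 | 0 |

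Eligibility (Section 6.1.1) does not require a previous socket, so a before-after pair cannot be assumed either.

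**4. The SD.** The formula needs a within-patient SD, and Section 6.2 labels 0.998 a population SD. If it is a between-patient SD and a patient's two scores correlate at r, the within-patient SD is 0.998 × √(1 − r), which is smaller for positive r. At an assumed r = 0.5, power with 19 patients would be 0.999 rather than 0.940. The mismatch would usually be conservative.

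**5. What 19 patients in a single arm can support** (one-sided 0.025; SDs of 1.5 and 2.0 are assumed).
- Error-free reference: SE = SD/√19, 18 df, margin 1.21.
- Historical sample of 50 (assumed, same SD): SE = SD × √(1/19 + 1/50), 67 df, margin 1.21. At SD 0.998, SE = 0.269 and noncentrality = 1.21/0.269 = 4.50.
- Mean above 7: noncentrality = (true mean − 7)/(SD/√19), 18 df, solved for 90% power.

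| SD | Power, error-free reference | Power, 50 historical | True mean for 90% power, lower limit above 7 |
|---|---|---|---|
| 0.998 | 0.999 | 0.993 | 7.79 |
| 1.5 | 0.914 | 0.839 | 8.18 |
| 2.0 | 0.704 | 0.600 | 8.57 |

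For contrast, a concurrent parallel trial at SD 0.998 needs 16 per arm (power 0.913), and 19 patients split 9/10 have power 0.70.

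**6. Bias in a historical reference.** If the reference is too low by b, the noncentrality at the margin is b/SE instead of 0. At SD 0.998, with the reference treated as error-free, b = 0.25 or 0.5 (assumed) raises the type I error from 0.025 to 0.18 or 0.54. With the assumed 50 historical patients and their standard error carried, it is 0.15 or 0.45.

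**The case against.** **The comparator may be defined elsewhere.** The protocol defers to a Clinical Investigation Plan, and an SAP may exist; neither was seen, nor were the pathway diagrams. Section 4 describes a dataset of past NHS fittings with outcome measures, which could serve as a reference although it is never named as one. This stands as a limit on scope: a reader might infer that no comparator exists at all, and the protocol shows only that it describes none. But an external reference would not turn the design into a crossover, so Section 6.2 would still be wrong.

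**The E-CRF field is generic.** A reader might infer that it records the study socket only. Its wording does not say so. What can be said is that no field is dedicated to a current-process score.

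**This is a usability study.** Section 6.2 declines a power analysis for the prosthetists. For the patients, it powers a non-inferiority comparison that Section 4.1 claims, so the objection does not reach this point.

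**19 is ample.** On the stated SD it is, against a reference that is fixed and unbiased. That is a different hypothesis from the one sized.

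**Conclusion.** The point holds as an internal contradiction between the sizing in Section 6.2 and the conduct in Sections 6.5, 6.6 and 6.8. The figure of 19 is correct arithmetic for a two-period crossover. Its power of 0.9 does not apply to the single arm described, and the non-inferiority objective in Section 4.1 cannot be tested from the data the protocol describes. The criterion of a score above 7 needs no comparator and is unaffected.

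Two stronger readings are not supported. One is that Stage Two recruits too few patients: 19 falls short for a concurrent parallel control, but gives power of 0.99 or more in a single arm at the stated SD. The other is that the population SD leaves the trial under-powered: with positively correlated scores the error runs the other way. That the data analysis section sets out no non-inferiority test is not counted here, since an SAP may contain it.

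The single-arm figures rest on the stated margin, one-sided 0.025, a true difference of 0 for the non-inferiority comparisons, and the assumed SDs and historical sample size shown.

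**What to change.** In Section 6.2, replace the crossover calculation with a single-arm description, restate power for it over a range of SDs, and choose one route before Stage Two starts.

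- **(a) Keep a non-inferiority comparison.** Name one current-process reference, for example existing comfort scores at the same fitting step, preferably not the ATFS training cases. Carry its standard error into the comparison, and test the lower one-sided 97.5% limit of ATFS mean minus reference against −1.21. Word the conclusion as non-inferior to historical scores, and state the risk from a reference that is biased low.
- **(b) Drop the non-inferiority claim.** Reword Section 4.1 to rest on the criterion of a score above 7, for example a lower 97.5% limit of the mean above 7. Section 7 summarises scores by number and percentage, so a proportion above 7 is another possible reading. The protocol should say which is meant and give power for it.

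The cost is protocol wording and a new power statement. Route (a) adds a data extraction, subject to data-access approval, because the consent described covers participants only. No extra patients are needed if the SD is near 0.998; at the larger assumed SDs, route (a) falls below 90% power, and route (b) needs a higher true mean. Under either route the conclusion is weaker than a concurrent or within-patient comparison.

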6.3 Recruitment

Group A – Prosthetists

Convenience sampling will be used to recruit prosthetists who are interested in taking part at Bristol, Norwich and Cambridge NHS Opcare prosthetic services.

Group B – Adults with limb loss

Convenience sampling will be used to identify participants to take part in the trial. All patients who meet the inclusion criteria and have been referred for limb fitting at one of the participating NHS prosthetics centres, or contact one of the three centres for an assessment appointment within the study period will be invited to take part in the trial. An invitation letter and Participant Information Sheet (PIS) will be sent from participating clinics to potential participants ahead of their assessment appointment to allow them sufficient time to consider taking part in the study prior to the appointment.

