The socket represents the interface between the residual limb and prosthetic componentry. However advanced the componentry, if the socket interface lacks the necessary balance of firm limb-device coupling and comfort, the limb's function will be impaired to the extent that the person may choose not to use the prosthetic limb. This situation is indeed common: rejection rates are $31\%^4$. Sockets are designed by a prosthetist, in a process that aims to optimise comfort, stability and mobility for the prosthesis user. In addition, socket fit is dependent on multifactorial patient differences including limb shape, soft tissue stiffness, regional tolerance to load and comorbidities. Sockets are not a 1:1 match of limb shape; instead, the prosthetist makes modifications, or "rectifications," to the baseline limb shape. This is intended to load pressure-tolerant limb regions, and off-load pressure-sensitive sites, to produce a secure and comfortable interface between patient and prosthesis. Rectification is a highly complex, skill- and experience-based process, yet there is little objective guidance or evidence to support prosthetists who require years of training and experience to hone their skills. This complexity leads to multiple iterative re-fittings, with an average of 9 visits to prosthetists in the first postoperative year⁵. Whilst some adjustment and re-fitting is inevitable as the residual limb stabilises in shape and volume, the clinical community is calling for tools to support them in taking a more evidence-based approach to the fitting process, to tackle these service inefficiencies and their socioeconomic impacts.

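### Stage Two's 19 is sized as within-patient pairs, but recruitment admits first-time prosthesis users, who cannot supply a pair, and the stage closes on 19 designs, not 19 pairs

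*Protocol*

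**What the plan says.** - **Aim.** Section 4.1 has Stage Two collect comfort scores "to demonstrate non-inferiority compared to the current process (without the support of the ATFS"), and also show scores above 7 and compare design time.
- **Size.** Section 6.2: "A sample size of 19 will be recruited for Stage Two". On the method: "This sample size was determined using a noninferiority result for a crossover group trial with normal socket comfort score data". The inputs are "power: 0.9, significance level: 0.025, Mean Difference: 0", a margin of 1.21 and a standard deviation of 0.998. A further 10% is added for uncertainty in the data used.
- **Who may enter.** Section 6.1.1 asks that a Group B patient be an adult with a transtibial amputation, able to consent, and "Deemed ready to cast for a new prosthesis by the clinical team as per usual care at the prosthetic centre". Earlier socket use and time since amputation are not mentioned. Section 6.3 invites "All patients who meet the inclusion criteria and have been referred for limb fitting at one of the participating NHS prosthetics centres", and also patients who contact a centre for an assessment.
- **What each patient receives.** Under section 6.6 there is one design process, aided by the ATFS, in place of the clinic's standard CAD/CAM process.
- **When the stage ends.** Under section 6.8, when the ATFS has supported socket design for 19 patients.
- **What is recorded.** The E-CRF in section 16.2 has one item for comfort score(s). It has none for user status, amputation date or a score on an earlier socket.

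**The concern.** A crossover size counts patients who are each measured under both conditions. The study makes no current-process socket, so the only within-patient comparator available is a socket the patient already had. A first-time user has none. Such patients are eligible in any proportion, and each one uses up a place among the 19 without adding to the paired comparison. The 10% addition is not assigned to them, and the closing rule does not check for pairs.

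A second, smaller issue concerns the limb. Section 4 says: "Whilst some adjustment and re-fitting is inevitable as the residual limb stabilises in shape and volume". A new user's score, taken at a fitting after the scan, may partly reflect limb change. If user status is not recorded with the result, the share above 7 cannot be shown separately for new and established users.

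At stake is whether the stated power of 0.9 applies to the number of patients who can inform the non-inferiority conclusion.

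**Working it through.** **Inputs (section 6.2).** Margin 1.21; standard deviation 0.998; true difference 0; power 0.9; significance level 0.025, taken as one-sided; 10% addition.

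**Step 1: reproduce the 19.** Treat 0.998 as the standard deviation of a single score, so the difference has SD 0.998 × √2 = 1.411.

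- Normal approximation: n = 2 × 0.998² × (1.960 + 1.282)² / 1.21² = 14.3, so 15 pairs. Adding 10% gives 15 × 1.1 = 16.5, or 17. This does not match.
- Exact paired t (noncentral t, n − 1 degrees of freedom, noncentrality 1.21 × √n / 1.411): the smallest n with power of at least 0.9 is 17 (power 0.912). Adding 10%: 17 × 1.1 = 18.7, or 17 / 0.9 = 18.9. Both round up to **19**, the protocol's figure.
- Taking 0.998 directly as the SD of the difference needs only 10 pairs, or 11 to 12 after the addition. This does not match either.

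The 19 is therefore consistent with 17 patients who each supply a pair, plus two.

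**Step 2: power by number of pairs, same method.**

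| Patients with a pair | Without a pair (of 19) | Share without | Power |
|---|---|---|---|
| 19 | 0 | 0% | 0.942 |
| 17 | 2 | 11% | 0.912 |
| 16 | 3 | 16% | 0.893 |
| 15 | 4 | 21% | 0.870 |
| 13 | 6 | 32% | 0.810 |
| 10 | 9 | 47% | 0.676 |

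Two unpaired patients can be absorbed. The third takes power below 0.9.

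**Step 3: what keeping 17 pairs would need.** The protocol gives no share of first-time users, so the shares here are assumptions. Total recruitment is 17 / (1 − share), rounded up: 19 at 10%, 22 at 20%, 25 at 30%, 29 at 40% and 34 at 50%.

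**The case against.** - **No pair is scheduled for anyone.** The protocol never names an earlier socket as the comparator, and no step collects a score on one. The undefined comparator affects all 19 patients, and the first-time-user issue sits inside it. This stands. Naming an earlier socket as comparator would still leave the first-time users unpaired, so the point does not disappear.
- **A historical or external comparator would let first-time users count.** A reader might infer that they can inform no comparison at all. The documents do not support that: section 4 refers to outcome measures from previous NHS fittings, and section 6.2 takes its SD from the training dataset. Such a comparison would not be the crossover behind the 19, however, and would need its own calculation.
- **First-time users are not wasted.** They inform the above-7 criterion, design time and usability. A reader might infer that they should be excluded. That does not follow: including them is a choice about generalisability, and the early fitting burden is part of the protocol's own rationale.
- **The share is unknown.** Section 6.3 speaks of referral for limb fitting and does not say how many patients are first-time users. The loss could be nil.
- **The limb-change argument is limited.** The average of 9 visits in section 4 rests on a reference whose title concerns transfemoral prostheses. Patients must already be judged ready to cast, and established users' limbs can change too. It supports recording user status, not restricting entry.
- **The E-CRF may not be the only record.** Section 10 describes it largely as a check that activities were done, and the Clinical Investigation Plan is not shown. The missing items do not prove that the information is unavailable in clinic records.

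**Conclusion.** The point holds for the within-patient non-inferiority comparison. The sample size assumes pairs, while eligibility, the one-socket procedure and the closing rule together allow unpaired patients to be counted as if they were pairs. Eligibility, the closing count and the case report form are protocol content.

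The margin for loss is two patients of 19; power is 0.893 after three and 0.676 after nine. These figures rest on the SD of the difference being 0.998 × √2, which recovers the stated 19, and on a true difference of zero. A reader might infer that the study is in fact underpowered. The documents do not show that, because the share of first-time users is not given. What they show is that nothing protects the stated power.

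**What to change.** Keep eligibility open and change the following:

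1. State the source and timing of the current-process comfort score.
2. Record on the E-CRF first-time or established status, date of amputation, and any current-process score with its date.
3. Base the within-patient non-inferiority conclusion only on patients with that score, and restate its power for the number of pairs obtained.
4. Report first-time users separately, including for the above-7 criterion.
5. If a historical or external comparator is used instead, re-derive the sample size for an unpaired comparison.

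If an earlier socket is the comparator, the protocol should acknowledge that a score on an old, worn socket may favour the new one and so make non-inferiority easier to show. Recording its date lets the reader judge this.

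**Cost.** Three E-CRF items and a few sentences. The non-inferiority claim is then limited to established users, and its stated power may be lower than 0.9. Restricting entry to established users is not advised: it would slow accrual and remove patients who serve the other Stage Two aims.
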